5.4. Screen Failures

Screen failures are defined as participants who consent to participate in the clinical study but are not subsequently randomly assigned to study drug.

Tests with results that fail eligibility requirements may be repeated once during screening if the investigator believes the result to be in error. Additionally, a participant who fails screening may repeat the screening process 1 time if the investigator believes that there has been a change in eligibility status. Participants who rescreen must re consent and be assigned a new participant number.

All screening procedures with the possible exceptions noted below will be repeated during rescreening. The participant must meet all the eligibility criteria at the time of rescreening in order to qualify for the study. There is no minimum period of time a participant must wait to rescreen for the study. If the participant had a complete initial screening evaluation including the following assessments, these tests will not be required to be repeated for rescreening, provided the conditions noted in Sections 5.1 and 5.2 are met, there are no changes in the participant's medical history that would warrant retesting, and no more than 90 days have passed:

- HBV, HCV, and HIV serology
- IGRA (QTF Gold test [or IGRA equivalent such as T-SPOT® test] and/or local PPD skin test, if required)
- ECG

5.5. Replacement of Participants

No participants will be replaced at any time during this study. However, as noted in [Appendix E](#), due to the evolving situation of the COVID-19 pandemic, the sponsor may decide to recruit additional participants in the study beyond the expected number (eg, if a substantial number of participants withdraw early from the study).

5.6. Data Safety Monitoring Board

This study will use an internal DSMB to monitor safety as detailed in the DSMB charter.

The voting members of the committee will be blinded to participants' treatment assignment for the initial safety review; however, the DSMB members may request unblinding at any time.

The members of the DSMB will not be involved with the study in any other way and will have no competing interests that could affect their roles with respect to the study.

The DSMB will make recommendations to the study team regarding steps to ensure both participant safety and the continued ethical integrity of the study. Specific details regarding composition, responsibilities, and governance, including the roles and responsibilities of the various members and the sponsor, and requirements for the proper documentation of DSMB reports, meeting minutes, and recommendations will be described in the DSMB charter, which will be reviewed and approved by all DSMB members.

5.7. Cardiovascular Adjudication Committee

An independent committee of physician experts in cardiovascular adjudication will be utilized to assess potential cardiovascular and thromboembolic AEs. Details will be described in a separate CAC charter.

6. STUDY TREATMENT

6.1. Study Treatments Administered

Table 7 presents the study treatment information. Participants will record study drug administration in an eDiary. Study drug administration and any interruptions and discontinuation of treatment will also be recorded in the eCRF. Further information regarding study drug administration is provided in Appendix C.

The COVID-19 global pandemic may present challenges to the normal conduct of this study, requiring the outline of potential mitigation strategies described in Appendix E.

Table 7: Study Treatment Information

Study treatment name:	Povorcitinib	Povorcitinib matching placebo
Mechanism of action:	JAK inhibitor	Not applicable
Dose formulation:	Tablet oral	Matching tablet
Unit dose strength(s) / dose level(s):	15 mg = 1 povorcitinib 15-mg tablet and 4 placebo tablets 45 mg = 3 povorcitinib 15-mg tablets and 2 placebo tablets 75 mg = 5 povorcitinib 15-mg tablets	Matching placebo = 5 tablets
Administration instructions:	Povorcitinib or matching placebo will be taken orally QD with water at approximately the same time each day unless otherwise instructed by site personnel. The study drug can be taken with or without food. Note: Dose will be administered at the study site during visits. Participants will withhold self-administration on the days of those visits.	
Packaging and labeling:	Povorcitinib will be provided as 15 mg tablets; placebo tablets will match the povorcitinib tablets in smell, taste, and appearance. Tablets will be packaged in blister cards. Each blister card will be labeled as required per country requirement.	
Storage:	Ambient (15°C-30°C/59°F-86°F).	
Status of treatment in participating countries:	Investigational	

6.2. Background Therapy

All participants will be required to remain on a concurrent, stable dose of second-generation H1 antihistamine as background therapy (SOC), which will not be changed throughout the study.

6.3. Preparation, Handling, and Accountability

The investigator or designee must confirm appropriate temperature conditions have been maintained during transit for all study treatments received and any discrepancies are reported and resolved before use of the study treatment.

Only participants enrolled in the study may receive study treatment, and only authorized site staff may supply or administer study treatment. All study treatment must be stored in a secure, environmentally controlled, and monitored (manual or automated) area in accordance with the labeled storage conditions with access limited to the investigator and authorized site staff.

The investigator or designee is responsible for study treatment accountability, reconciliation, and record maintenance (ie, receipt, reconciliation, and final disposition records). Inventory and accountability records must be maintained and readily available for inspection by the study monitor and are open to inspection at any time by any applicable regulatory authorities. The investigator or designee must maintain records that document the following:

- Delivery of study drug to the study site.
- Inventory of study drug at the site.
- Participant use of the study drug, including tablet counts from each supply dispensed.
- Return of study drug to the investigator or designee by participants.

The investigational product must be used only in accordance with the Protocol (see [Appendix C](#)). The investigator or designee will also maintain records adequately documenting that the participants were provided the specified study drug. These records should include dates, quantities, and any available batch or serial numbers or unique code numbers assigned to the investigational product and study participants.

Completed accountability records will be archived by the site. The investigator or designee will be expected to collect and retain all used, unused, and partially used containers of study drug until verified by the study monitor (unless otherwise agreed to by the sponsor). At the conclusion of the study, the investigator or designee will oversee the destruction of any remaining study drug according to institutional SOPs. If, however, local procedures do not allow on-site destruction, shipment of the study drug back to the sponsor is allowed. In this case, the site should (where local procedures allow) maintain the investigational supply until the study monitor inspects the accountability records in order to evaluate compliance and accuracy of accountability by the investigative site. At sites where the study drug is destroyed before monitor inspection, the monitors rely on documentation of destruction per the site SOP.

Further guidance and information for the final disposition of unused study treatments are provided in the study materials provided to the sites.

6.4. Measures to Minimize Bias: Randomization and Blinding

This is a randomized, double-blind, placebo-controlled study.

All participants will be centrally assigned to study treatment using an IRT system. Study drug will be dispensed at the study visits summarized in the SoA (see [Table 3](#)). Returned study drug should not be redispensed to the participants. Full details will be provided in the IRT Study Reference Manual.

The sponsor will be blinded to the treatment throughout the PC period and will be unblinded at the time of primary analysis. Participants and investigators will remain blinded to each participant's treatment assignment throughout the study. This is implemented to minimize bias throughout the PC and EXT periods of the study.

Emergency unblinding will occur if an AE requires the investigator to be made aware of the participant's treatment assignment (see emergency unblinding procedures in [Section 9.7](#) and refer to the Study Reference Manual).

6.5. Study Treatment Compliance

Compliance with all study-related treatments should be emphasized to the participant by the site personnel, and appropriate steps should be taken to optimize compliance during the study.

6.5.1. Compliance With Povorcitinib/Placebo

Compliance with study drug will be calculated by the sponsor based on the drug accountability (eg, tablet counts) documented by the site staff and monitored by the sponsor/designee. Participants will be instructed to bring all unused study drugs with them to the study visits in order for site personnel to conduct tablet counts to assess study drug accountability.

Compliance with study drug will be calculated for the PC and EXT periods based on the following:

Within the PC period:

- The first dose will occur on Day 1 (baseline).
- The last dose will occur on the day of the Week 12 visit or the day of the last study drug administration known to the investigator (or designee) as reported in the EDC for participants who prematurely discontinue study treatment or are lost to follow-up.

Within the EXT period:

- The first dose will occur the day after the Week 12 visit.
- The last dose will occur on the day of the Week 36 visit or the day of the last study drug administration known to the investigator (or designee) as reported in the EDC for participants who prematurely discontinue study treatment or are lost to follow-up.

Participants' compliance must be within 80% to 120% assessed at each study visit by the investigator (or designee). If outside of this range, it will be considered a Protocol deviation. Participants consistently noncompliant with the study drug may be withdrawn from the study. The decision on withdrawal will be made by the investigator after consultation with the sponsor, and relevant correspondence will be archived in the site study file.

6.5.2. Compliance With Background Therapy

Participants will be instructed to record background therapy administration in the eDiary from the screening visit until completion of the post-treatment follow-up visit (EOS). Compliance with background therapy will also be documented in the participant's study source documentation and monitored by the investigator (or designee).

6.6. Dose Modifications

No dose modifications will be allowed during the study. In some circumstances, it may be necessary to temporarily interrupt treatment with study drug as a result of AEs or laboratory abnormalities that have an unclear relationship to the study drug.

Decisions by the investigator (or designee) regarding dose interruption/discontinuation of study drug should be made using clinical judgment, taking into account relatedness of the AE to the study drug and the participant's underlying condition. The sponsor (or designee) may be consulted as needed. Instructions for dose interruption or discontinuation of study drug are outlined in Sections 6.6.1 and 6.6.2.

6.6.1. Criteria and Procedures for Dose Interruptions and Adjustments of Study Drug

Safety concerns should be discussed with the sponsor immediately upon occurrence or awareness to determine if the participant should continue or discontinue study drug.

Treatment with study drug may be interrupted for up to 28 days, unless otherwise specified in the Protocol or a longer period is approved by the sponsor (or designee), to allow for resolution of toxicity. The principal investigator (or designee) should contact the sponsor to discuss the case of any participant whose treatment has been interrupted for more than 21 days (but less than 28 days) before restarting treatment. Participants may resume treatment if no medical condition or other circumstance exists that, in the opinion of the investigator, would make the participant unsuitable for further participation in the study.

Guidelines for interruption, restarting, and discontinuation of study drug are outlined in [Table 8](#) as well as in [Appendix E](#) (for COVID-19) and Section 6.6.1.6 (for emergency and elective surgeries).

Table 8: Guidelines for Interruption, Restarting, and Discontinuation of Study Drug

Laboratory Value	Action Taken
Chemistry	
ALT and/or AST is $> 3.0 \times < 20$ ULN	
Step 1: Interrupt study drug.
 
Step 2: Confirm whether potential Hy's law criteria have been met (see Appendix D), following applicable procedures. If potential Hy's law criteria are not met, proceed to Step 3.
 
Step 3: Repeat ALT/AST assessments weekly for up to 3 weeks or until ALT and/or AST results are $< 3.0 \times$ ULN and then restart study drug at the same dose.
 
If ALT and/or AST result(s) do not decrease to $< 3.0 \times$ ULN after 3 weeks of drug interruption, study drug will be permanently discontinued, and the participant will follow EOT visit procedures; a post-treatment follow-up visit (EOS) is also recommended.
 
If the dose has been interrupted/restarted in 2 other instances due to ALT and/or AST results, and ALT and/or AST results are $> 3.0 \times$ ULN for a third time, study drug will be permanently discontinued, and the participant will follow EOT visit procedures; a post-treatment follow-up visit (EOS) is also recommended.
 
In parallel to the participant starting the post-treatment follow-up period, the investigator, in collaboration with the medical monitor, will determine further steps.

ALT and/or AST is $> 20.0 \times$ ULN	
Step 1: Discontinue study drug administration and have the participant follow EOT visit procedures; a post-treatment follow-up visit (EOS) is also recommended.
 
Step 2: In parallel to the participant starting the post-treatment follow-up period, the investigator, in collaboration with the medical monitor, will determine further steps.

CPK is $> 5.0 \times$ ULN	
Step 1: Evaluate if there are symptoms suggestive of myositis or rhabdomyolysis. Additionally, the investigator may repeat the test for confirmatory purposes.
 
Step 2: If there are no symptoms suggestive of myositis or rhabdomyolysis, the participant may continue study drug at the investigator's discretion. Appropriate monitoring should be conducted.
 
Step 3: If symptoms suggestive of myositis or rhabdomyolysis are identified, interrupt study drug and contact the medical monitor (or designee).

Table 8: Guidelines for Interruption, Restarting, and Discontinuation of Study Drug (Continued)

Laboratory Value	Action Taken
Hematology	
Platelet count is $< 50 \times 10^9/L$	
Step 1: Interrupt study drug administration.
 
Step 2: Repeat platelet count assessment promptly, within 7 days, to confirm value.
 
Step 3: Repeat platelet count assessment weekly until platelet count reaches $\geq 100 \times 10^9/L$ and then restart study drug at the same dose.
 
If platelet count does not increase to $\geq 100 \times 10^9/L$ after 3 weeks of drug interruption, study drug will be permanently discontinued, and the participant will follow EOT visit procedures; a post-treatment follow-up visit (EOS) is also recommended.

ANC is $< 1.0 \times 10^9/L$	
Step 1: Interrupt study drug administration until the toxicity has resolved to $\geq 1 \times 10^9/L$ or the baseline value.
 
Step 2: Restart study drug at the same dose and monitor as clinically indicated.

Hemoglobin is 8 to < 9 g/dL or > 2-g/dL decrease from baseline.
 
Note: If the decrease results in a value < 8 g/dL, then follow the guidance below.
	
Step 1: Interrupt study drug administration until the toxicity has resolved, with hemoglobin meeting the criteria of ≤ 2-g/dL decrease from baseline.
 
Step 2: Evaluate medical history to determine if the decrease in hemoglobin was likely related to underlying disease or investigational drug.
 
Step 3: Restart study drug and monitor as clinically indicated.

Hemoglobin is < 8 g/dL	Discontinue study drug administration and have the participant follow EOT visit procedures; a post-treatment follow-up visit (EOS) is also recommended.
Creatinine ≥ 2 mg/dL	
Step 1: Repeat the test for serum creatinine (with the participant in a euvolemic state) within 7 days to confirm the result.
 
Step 2: If the results of the repeat testing confirms creatinine ≥ 2 mg/dL, interrupt study drug.
 
Step 3: Perform creatinine assessment weekly for up to 3 weeks, or until creatinine returns to less than or equal to the participant's baseline. Study drug may be restarted.
 
If creatinine does not decrease to less than or equal to the participant's baseline after 3 weeks of drug interruption, study drug will be permanently discontinued and the participant will follow EOT visit procedures; a post-treatment follow-up visit (EOS) is also recommended.

Table 8: Guidelines for Interruption, Restarting, and Discontinuation of Study Drug (Continued)

Laboratory Value	Action Taken
Other toxicities	

Serious infection/opportunistic infection (defined as any infection or opportunistic infection meeting SAE criteria [see Section 9.2])
	
Step 1: Interrupt study drug administration.
 
Step 2: Initiate prompt diagnostic testing appropriate for an immunocompromised participant. As appropriate, antimicrobial therapy should be initiated, and the participant should be closely monitored.
 
Step 3: Restart study drug once the infection has been successfully treated and closely monitor as clinically indicated.

New evidence of TB
	
Discontinue study drug administration and have the participant follow EOT visit procedures; a post-treatment follow-up visit (EOS) is also recommended.

Herpes zoster
	
Consider interrupting study drug administration until the episode resolves.

Thrombosis events
	
Step 1: Promptly evaluate and treat appropriately if symptoms of thrombosis develop.
 
Step 2: Discontinue study drug administration if any of the following diagnoses is confirmed:
 
 • Venous thrombosis (such as but not limited to deep vein thrombosis and pulmonary embolism) • Arterial thrombosis (such as but not limited to MI and stroke) • Any other thromboembolic event 
Have the participant follow EOT visit procedures; a post-treatment follow-up visit (EOS) is also recommended.


Any malignancy except nonmelanoma skin cancer or carcinoma in situ of the cervix (see Section 6.6.1.5 for additional management guidance)
	
Discontinue study drug administration and have the participant follow EOT visit procedures; a post-treatment follow-up visit (EOS) is also recommended.

Any Grade 1 or Grade 2 toxicity
	
Continue study drug administration and treat the toxicity; monitor as clinically indicated.

Any Grade 3 toxicity (except if specifically described in this table) if clinically significant and not manageable by supportive care
	
Step 1: Interrupt study drug up to 2 weeks (14 days), until toxicity resolves to ≤ Grade 1.
 
Step 2: Restart study drug and monitor as clinically indicated.

Any other Grade 4 toxicity
	
Discontinue study drug administration and have the participant follow EOT visit procedures; a post-treatment follow-up visit (EOS) is also recommended.

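### Protocol Table 8: for baselines below 11 g/dL, the hemoglobin restart number can already be met by the reading that stops the drug

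*Protocol*

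**What the plan says.** The hemoglobin row of Protocol Table 8 has two alternative triggers: "Hemoglobin is 8 to < 9 g/dL or > 2-g/dL decrease from baseline". Values below 8 g/dL go to a separate row that discontinues study drug.

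Step 1 of the row reads "Interrupt study drug administration until the toxicity has resolved, with hemoglobin meeting the criteria of" a fall of 2 g/dL or less from baseline. Step 2 is a review of medical history for the likely cause. Step 3 restarts the drug, with monitoring as clinically indicated. The row sets no absolute level for restart, no repeat test and no minimum hold.

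Two general provisions in Section 6.6.1 also apply. One concerns the sponsor: "Safety concerns should be discussed with the sponsor immediately upon occurrence or awareness to determine if the participant should continue or discontinue study drug". The other concerns resumption: "Participants may resume treatment if no medical condition or other circumstance exists that, in the opinion of the investigator" would make the participant unsuitable. Neither gives a hemoglobin value.

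Protocol Table 6 excludes screening hemoglobin below 10 g/dL, so 10.0 to 10.9 is eligible. SAP Section 4.1.3 takes baseline as the last nonmissing value on or before the day of first dose.

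**The concern.** The row stops the drug on an absolute level or on a relative fall, but the number that releases it is only relative. When the absolute level is the sole reason for stopping, the release number holds nothing back.

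The absolute band appears to be a deliberate extra protection. SAP Table 8 grades 80 to < 100 g/L as Grade 2, and the general rule in Protocol Table 8 for Grade 2 toxicity is to continue drug. The hemoglobin row departs from that rule by stopping at 8 to < 9 g/dL. For low-baseline participants the restart number does not enforce that stop, so each site, or the sponsor case by case, has to supply a floor, and the same value may be handled differently.

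A participant restarted inside the band meets the interruption trigger again at the next sample unless the value has risen. Section 6.6.2 lists recurrence of an event that led to interruption as a ground for permanent discontinuation. That is only a possible consequence, because a value that merely persists may not count as a recurrence.

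**Working it through.** There is no plan figure to reproduce; this is a check of the rule's logic.

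**Inputs.** Let B be baseline hemoglobin and H the current value, in g/dL.

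- Absolute trigger A: 8 ≤ H < 9 (Protocol Table 8)
- Fall trigger F: B − H > 2 (same row)
- Restart number R: B − H ≤ 2 (same row, Step 1)
- Eligible at screening: 10 or above (Protocol Table 6)

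**Logic.** R is the exact complement of F. A acting alone means A and not F, which is the same as A and R. So whenever A is the only trigger, R is already true. Since H < 9 and B ≤ H + 2, this requires B < 11. That is necessary but not sufficient: B = 10.5 with H = 8.2 is a fall of 2.3, and both triggers fire.

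**Grid at 0.1 g/dL, H from 8.0 to 8.9.** The lowest restart value is B − 2 under the current text, and the larger of B − 2 and 9 with a floor of 9.

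| B | A alone (R already met) | A and F together | Lowest restart value now | With floor of 9 |
|---|---|---|---|---|
| 10.0 | 10 | 0 | 8.0 | 9.0 |
| 10.1 | 9 | 1 | 8.1 | 9.0 |
| 10.2 | 8 | 2 | 8.2 | 9.0 |
| 10.3 | 7 | 3 | 8.3 | 9.0 |
| 10.4 | 6 | 4 | 8.4 | 9.0 |
| 10.5 | 5 | 5 | 8.5 | 9.0 |
| 10.6 | 4 | 6 | 8.6 | 9.0 |
| 10.7 | 3 | 7 | 8.7 | 9.0 |
| 10.8 | 2 | 8 | 8.8 | 9.0 |
| 10.9 | 1 | 9 | 8.9 | 9.0 |
| 11.0 | 0 | 10 | 9.0 | 9.0 |

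For B from 10.0 to 10.9 the totals are 10 + 9 + … + 1 = 55 cells with A alone and 0 + 1 + … + 9 = 45 with both. In the 45 the restart number does demand a rise, but only to 8.1–8.9, which is still inside the interruption band.

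**Spot checks.**

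- B = 10.4, H = 8.5: fall 1.9; interrupted, restart number already met.
- B = 10.5, H = 8.2: fall 2.3; interrupted, restart number met at 8.5.
- B = 11.0, H = 8.9: fall 2.1; interrupted, restart number met at 9.0. The rule works here.

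**Other laboratory rows of Table 8 with a numeric restart test.**

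- Platelets: stop below 50 × 10⁹/L. "Repeat platelet count assessment weekly until platelet count reaches" 100 × 10⁹/L or more, well above the trigger.
- ALT/AST: stop above 3.0 × ULN. "Repeat ALT/AST assessments weekly for up to 3 weeks or until ALT and/or AST results are" below 3.0 × ULN.
- Creatinine: stop at 2 mg/dL or more. "Perform creatinine assessment weekly for up to 3 weeks, or until creatinine returns to less than or equal to the" participant's baseline, which is stricter than the trigger for any baseline below 2 mg/dL.
- ANC: stop below 1.0 × 10⁹/L; restart at 1 × 10⁹/L or more "or the baseline value".

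Each of these restart numbers is tied to its own trigger. The hemoglobin number is tied to only one of its two.

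**The case against.** The strongest reply is that the row is more than its number. Step 1 asks for the toxicity to have resolved, and a value still inside the 8 to < 9 band has not plainly resolved. Step 2 comes before restart, safety concerns go to the sponsor, and resumption rests on the investigator's judgment. A careful site may well wait. This stands as far as it goes: the protocol does not order an immediate restart. But the row gives resolution a numeric meaning only through the fall test, and none of the other provisions names a level.

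A second reply is that the harm is bounded. The value is Grade 2, the default for Grade 2 is to continue, discontinuation below 8 g/dL is intact, and hematology is drawn at every scheduled visit. No endpoint, estimand or power figure is touched. All of that is correct and keeps the point modest. It does not explain why the row would stop the drug at a level and then set a restart number that ignores that level.

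Third, the comparison with ANC is not airtight. If Day 1 ANC were below 1.0 × 10⁹/L, the baseline alternative in that row could also be met at interruption. Table 6 excludes screening ANC below 1.5 × 10⁹/L, so this is remote.

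Fourth, recovery to the participant's own baseline is a defensible standard, and a fixed floor has a cost. The documents do not give that rationale, and the row's own trigger already applies a fixed level whatever the baseline.

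**Conclusion.** The concern holds. When hemoglobin of 8 to < 9 g/dL is the only trigger, which can happen only with a baseline below 11 g/dL, the row's single restart number is satisfied at the moment of interruption. This follows from the text alone, and Table 6 makes such baselines reachable.

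A floor of 9 would raise the lowest restart value by 11 − B: 1.0 g/dL at a baseline of 10.0, 0.6 at 10.4, 0.5 at 10.5, 0.1 at 10.9, and nothing from 11.0 upward.

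The documents do not say how often a baseline below 11 g/dL is followed by an on-treatment value of 8 to < 9, and probably few participants are affected. The grid assumes baseline equals or exceeds the screening limit of 10. Because baseline may be a Day 1 value, it could be lower, which would widen the range in which the restart number does nothing. The point is a correction worth making to a safety rule; it does not threaten the efficacy analysis.

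**What to change.** In Step 1 of the hemoglobin row, require both conditions before restart: hemoglobin of at least 9 g/dL and a fall of no more than 2 g/dL from baseline. This reuses the sponsor's own trigger value and alters the rule only for baselines below 11.0 g/dL.

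The cost is a one-row protocol change. Under Section 11.1, amendments that change the study design need health-authority and IRB/IEC approval before implementation. The clinical downside is a longer hold for a few low-baseline participants. Someone with baseline 10.0 and a stable value of 8.8 (fall 1.2) meets the present number but could not restart under the new one, and might reach the 28-day limit in Sections 6.6.1 and 6.6.2. With a Day 1 baseline below 9, the floor would ask for recovery above baseline. In both situations the existing provision for the sponsor to approve a longer interruption remains available.
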